17.4.3.5. Twelve-lead Electrocardiogram (ECG)

Individual subject results will be summarized categorically as normal, clinically significant abnormal, and not clinically significant abnormal by dose and presented in the subject data listings.

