The primary efficacy endpoint is subject-rated pain “right now” due to acute back spasm using an NRS (0-10) scale, from no pain to worst possible pain for the clinic visit on Day 14. This analysis will be performed using a linear test of trend across doses, using a mixed effect model for repeated measures. The model will include treatment and time as fixed effects, the treatment by time interaction, and the baseline NRS rating as a covariate. Differences in linear trend for each dose level versus placebo will be presented with 95% confidence intervals and associated p-values. The analysis performed for the primary endpoint will be repeated for the NRS at Day 4. Additional analyses for secondary efficacy endpoints will be conducted using repeated measures and analysis of covariance for continuous variables, a Wilcoxon Rank Sum test for categorical variables, and Kaplan-Meier analysis for time to pain relief.

Safety Analysis:

Safety measures will be summarized using descriptive statistics and listed for each subject.

Safety analysis will be based on all subjects randomized who receive at least 1 dose of the study medication. The safety analysis will evaluate AEs and additional safety parameters. The number and percentage of subjects experiencing at least one AE will be summarized by body system, preferred term, and treatment. If appropriate, AEs will also be summarized by intensity and relationship to study drug. Serious adverse events (SAEs), if any, will be tabulated.

Additional safety parameters will be assessed from summaries of physical examinations, 12-lead ECGs and vital signs. The 12-lead ECG results will be categorized as normal, clinically significant abnormal, and not clinically significant abnormal. Hematology, chemistry and urinalysis laboratory test results will be categorized relative to the normal ranges. The changes from baseline for each of these parameters from Screening to EOT will be presented. Complete listings and summary tables for all safety information including AEs, laboratory safety data, ECG, vital signs and physical examination will be included in the study report.

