18. Subjects who have had a recent history (less than 2 years before entering the study) of drug or alcohol abuse, or current positive urine drug screen. Alcohol abuse is defined as current consumption of more than three alcoholic beverages per day.
19. History of seizure disorder other than Infantile Febrile Seizures, family history of seizure, or history of head trauma with loss of consciousness.
20. Disability claim for back pain, or pending legal issue regarding back pain.
21. Subjects who have received treatment with an investigational product/device within 30 days prior to study entry.
22. Subjects who have a history of allergic reaction to tolperisone, eperisone, or other skeletal muscle relaxants, lidocaine, acetaminophen or NSAIDs or any components of these study medications.
23. Any other condition that, in the opinion of the Investigator, would adversely affect the subject's ability to complete the study or its measures.
24. Subjects who are unwilling to stop taking moderate to potent inhibitors of cytochrome P450 (CYP) isozymes CYP2D6 and CYP2C19, which are likely to cause drug interactions with tolperisone HCl (e.g., medications such as paroxetine and fluvoxamine).
25. Subjects who are a site staff member, relative, or friend of a site staff member or subjects in same household or who are related to each other.
26. Subjects with clinically significant cardiovascular disorders, such as ischemic heart disease, arrhythmias, poorly controlled hypertension, or history of acute myocardial infarction.
27. Subjects with QT interval greater than 480 milliseconds (msec) or greater than 450 msec if accompanied by a partial bundle branch block, or other clinically significant ECG abnormality at Screening in the judgement of the Investigator.
28. Subjects with diastolic blood pressure less than 50 mmHg or greater than 105 mmHg; sitting heart rate less than 50 beats per minute (bpm) or greater than 110 bpm (after approximately 3 minutes at rest); or heart rate by ECG less than 50 or greater than 110 bpm at Screening.

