6.4.2.4.1 Vital Signs

Vital signs will include the measurement of supine and standing blood pressure, orthostatic assessments, heart rate, respiratory rate, and body temperature. Vital signs will be measured on Day 1 (Screening/Baseline visit) and on Days 4, 14, and 28. Weight and height will be measured at Screening/Baseline only.

6.4.2.4.2 12-Lead Electrocardiogram

Standard 12-lead ECGs will be administered at the clinic on Day 1 (Screening/Baseline visit) and on Day 14 (Visit 3). Results are collected as normal or abnormal (not clinically significant or clinically significant) only.

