7.5.4.3 Pregnancy Test

Pregnancy test results will be presented in a by-subject data listing

7.5.4.4 *Alcohol Breathalyzer Test*

Alcohol breathalyzer test results will be presented in a by-subject data listing

7.5.4.5 *Urine Drug Screen*

Urine drug screen results will be presented in a by-subject data listing

7.5.5 *Vital Signs, Physical Findings, and Other Observations Related to Safety*

7.5.5.1 *Vital Signs*

Vital sign parameters including blood pressure (standing, supine, orthostatic), heart rate, respiratory rate and body temperature will be summarized by treatment group and for total tolperisone treated subjects. Descriptive statistics will be presented for results and change from baseline at each visit where parameters were scheduled to be collected.

Orthostatic blood pressure will be calculated as the standing minus supine measurement for both systolic and diastolic blood pressure.

Weight will be converted from lbs to kg using a conversion factor of 0.4536.

7.5.5.2 *12-Lead Electrocardiogram*

Twelve-Lead ECG interval parameters will be summarized categorically as normal, clinically significant abnormal, and not clinically significant abnormal by treatment group and for total tolperisone treated subjects at each scheduled visit.

7.5.5.3 *Neurological Examination*

Results of the neurological examination will be summarized categorically as improved, stable, and deteriorated by treatment group and for total tolperisone treated subjects at each scheduled visit.

7.5.5.4 *Physical Examination*

Results of the physical examination will be presented in subject data listings by subject and study visit.

7.5.5.5 *Concomitant and After-Treatment Medications*

Medications will be coded using the World Health Organization Drug Dictionary Enhanced (WHODDE), version B3 March 1, 2018. Medications entered on the eCRF will be mapped to Anatomic Therapeutic Chemical (ATC) drug class (level 4) and drug name.

Concomitant and after-treatment medications will be summarized separately for the Safety Population. The study phase of each medication will be determined programmatically based on medication start and end dates. A prior medication is defined as any medication administered prior to the date of the first dose of study drug. A concomitant medications is defined as any

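### The synopsis promises ECG change from Screening to end of treatment, but no planned table gives the number of subjects per dose whose ECG became newly abnormal or worse

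*Protocol*

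**What the plan says.** **Synopsis, Safety Analysis.** The ECG sentence reads "The 12-lead ECG results will be categorized as normal, clinically significant abnormal, and not clinically significant abnormal". A sentence on categorising laboratory results against normal ranges follows, and then: "The changes from baseline for each of these parameters from Screening to EOT will be presented".

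**Protocol 17.4.3.5.** "Individual subject results will be summarized categorically as normal, clinically significant abnormal, and not clinically significant abnormal by dose"; the sentence ends "by dose and presented in the subject data listings". It mentions no change from baseline.

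**SAP 7.5.5.2.** "Twelve-Lead ECG interval parameters will be summarized categorically as normal, clinically significant abnormal, and not clinically significant abnormal by treatment group", with the time basis given as "by treatment group and for total tolperisone treated subjects at each scheduled visit". It mentions no cross-tabulation against baseline.

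**SAP 6.4.2.4.2.** On what is captured: "Results are collected as normal or abnormal (not clinically significant or clinically significant) only". No numeric intervals are available for analysis.

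**Protocol 9.2, exclusion 27.** Besides its QT limits, it bars any "other clinically significant ECG abnormality at Screening in the judgement of the Investigator". A subject whose abnormal ECG is judged not clinically significant, and whose QT is within the limits, can enrol.

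**SAP 4 and 7.7.1.** SAP 4 undertakes to explain differences between the protocol's methods and its own. SAP 7.7.1 lists changes for sleepiness, daily activities and medication helpfulness, and none for ECG.

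**The concern.** Each subject has one ECG before dosing and one at Day 14 or early termination, read into the same three categories. The safety question is how many subjects at each dose had an ECG that got worse on treatment. A Day 14 count does not answer it, because the not clinically significant row mixes abnormalities present at entry with new ones, and subjects who revert to normal offset subjects who turn abnormal.

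The other safety measures are handled differently. Change from baseline is planned for laboratory values (Protocol 17.4.3.3, SAP 7.5.4.1) and vital signs (Protocol 17.4.3.4, SAP 7.5.5.1), and the neurological examination is recorded as a change status (SAP 6.4.2.4.3). ECG has neither, and without interval values a shift in means cannot stand in.

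Safety is a secondary objective of a study meant to choose the Phase 3 dose. Protocol 7.1 describes sodium and, to a lesser extent, calcium channel blockade, so ECG by dose is of natural interest.

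**Working it through.** The documents give no figure to reproduce, so the check is a comparison of text followed by two short calculations.

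**1. Planned ECG displays**

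| Place | Counts per category | Change or shift | Listing |
|---|---|---|---|
| Synopsis, Safety Analysis | yes | yes, on the plain reading | yes |
| Protocol 17.4.3.5 | yes, by dose | no | yes |
| SAP 7.5.5.2 | yes, by group and scheduled visit | no | through the general rule in SAP 7.1.1 |
| SAP 7.7.1 and 7.7.2 | not mentioned | omission not declared | not mentioned |

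The per-visit layout is the SAP's wording; Protocol 17.4.3.5 says only that results are summarised by dose.

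**2. What two counts can tell us.** Let n be subjects with both ECGs, B the number abnormal at baseline and D the number abnormal at Day 14. The number newly abnormal lies between max(0, D − B) and min(n − B, D). Take n = 80, the planned arm size, with no ECG missing. B and D are assumptions, because the documents give no ECG abnormality rates. With D = B:

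| B (share of 80) | Normal at entry | Newly abnormal: possible range | As share of those normal at entry |
|---|---|---|---|
| 4 (5%) | 76 | 0 to 4 | 0 to 5% |
| 8 (10%) | 72 | 0 to 8 | 0 to 11% |
| 16 (20%) | 64 | 0 to 16 | 0 to 25% |
| 24 (30%) | 56 | 0 to 24 | 0 to 43% |
| 32 (40%) | 48 | 0 to 32 | 0 to 67% |

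If four more are abnormal at Day 14 than at entry (B = 24, D = 28), the range is 4 to 28 of 56, or 7% to 50%. The counts never identify the number, but the uncertainty is small when few subjects enter with an abnormal ECG.

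**3. Effect on the comparison with placebo.** Let b be the share abnormal at entry, r the share of those still abnormal at Day 14, and p the share of initially normal subjects who turn abnormal. The Day 14 abnormal share is b·r + (1 − b)·p. Randomisation balances b in expectation. If r is also the same in both arms, the difference between arms is (1 − b)(p₁ − p₀).

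With assumed values r = 0.80, p₀ = 0.05 and p₁ = 0.20, a true difference of 15 points:

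- b = 0.05: 0.0400 + 0.0475 = 8.75% against 0.0400 + 0.1900 = 23.0%; difference 14.25 points.
- b = 0.10: 0.080 + 0.045 = 12.5% against 0.080 + 0.180 = 26.0%; difference 13.5 points.
- b = 0.30: 0.240 + 0.035 = 27.5% against 0.240 + 0.140 = 38.0%; difference 10.5 points.
- b = 0.40: 0.320 + 0.030 = 35.0% against 0.320 + 0.120 = 44.0%; difference 9.0 points.

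The counts keep a share 1 − b of the difference: 95% to 60% over this range. That is dilution, not disappearance. No power figure is offered, because no test of ECG results is planned and every rate is assumed.

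**The case against.** **The listings show the pairs.** Protocol 17.4.3.5 puts ECG results in the subject listings. This stands, so individual changes are not lost. It does not give a count per dose, which a reader would have to build by hand for about 400 subjects.

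**Important changes can become adverse events.** Protocol 16.1 allows a shift that the investigator considers clinically important to be an adverse event, and treatment-emergent events are tabulated by group. This also stands, in part, since it depends on the investigator's judgement.

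**The clinically significant row is largely clean.** Exclusion 27 bars such ECGs at Screening, so those seen at Day 14 are nearly all new. This stands, except possibly for subjects enrolled before Amendment 1 added the criterion; the documents do not say how many there were.

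**The synopsis may mean laboratory results only.** The promise directly follows the laboratory sentence, and applied to the whole paragraph it would also cover physical examinations, which are only listed. That reading is possible. The plain reading still includes ECG: it is categorised in the same run of sentences and is scheduled at exactly Screening and end of treatment.

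**A stronger inference is tempting.** A reader might conclude that new ECG abnormalities are hidden, or that a dose-related rise could look like no change against placebo. The documents do not support this. Offsetting by reversions affects the change within an arm. Between randomised arms the difference shrinks by the factor above, and it could cancel fully only if the drug also made entry abnormalities revert more often, which nothing in the documents suggests.

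**Conclusion.** The point holds, as a minor one. A presentation promised in the synopsis, on its plain reading, is missing from Protocol 17.4.3.5 and SAP 7.5.5.2 without being declared. As a result no planned table gives the number of subjects per dose whose ECG became newly abnormal or worse. What is lost is mainly movement between normal and not clinically significant abnormal.

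The absence of the table is a matter of text and rests on no assumption. Its size depends on how many subjects enter with an abnormal ECG, which the documents do not state. Amendment 1 aims at a generally healthy population, so entry rates of 5% to 10% are as plausible as the higher ones, and there the loss is small. No efficacy conclusion depends on it.

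**What to change.** In Protocol 17.4.3.5 and SAP 7.5.5.2, add a shift table of baseline category by Day 14 category, and by Day 14/ET category, for each treatment group and for total tolperisone. Show n (%) newly abnormal or worse than baseline, with subjects who have both ECGs as the denominator. If the sponsor prefers not to add it, declare the omission in SAP 7.7.1 and clarify which parameters the synopsis sentence covers.

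At the same time, reconcile the reference to interval parameters in SAP 7.5.5.2 with SAP 6.4.2.4.2, under which only the overall reading is collected.

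The cost is one extra table from data already captured, with no new procedure and no burden on subjects.

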17.4.3.6. Physical and Neurological Examination

Neurological examination results will be summarized in frequency tables by dose. Physical and neurological examination results will be presented in subject data listings.

17.4.4. DNA Genotyping

Results will be examined and summarized for CYP450 2D6 polymorphism, dose-response, and AE profile.

17.4.5. Pharmacokinetic Analysis

Details of the PK and associated statistical analyses will be included in a separate population PK Statistical Analysis Plan.

18. BIOLOGICAL SPECIMENS

Whole blood samples and urine samples will be collected as outlined in the Schedule of Procedures ([Table 2](#)) for clinical chemistry, hematology, urinalysis, and optional PK and DNA genotyping.

It is the responsibility of the Investigator to ensure that all personnel who will be handling, packaging, and/or shipping clinical specimens act in conformance with International Air Transport Association (IATA) regulations relating to the handling and shipping of hazardous goods.

19. CLINICAL AND LABORATORY DATA COLLECTION

19.1. Electronic Case Report Forms (eCRF)

An eCRF will be completed for each subject. All appropriate subject data gathered during the study will be recorded in English on these forms.

Whenever possible, all information requested on an eCRF should be completed. If information is not available, it should be documented as such.

The completed eCRFs for this study are the property of Neurana Pharmaceuticals, Inc. and should not be made available to third parties, except for authorized representatives of appropriate health/regulatory authorities, without written permission from Neurana Pharmaceuticals, Inc.

19.2. Electronic Patient Reported Outcomes (ePRO)

The ePROs will be collected in an electronic capture device (tablet and smartphone/use of trial application) that will be used at the clinic and by the subject at home/away from clinic to record pain assessments and other secondary endpoint assessments. A study-provisioned tablet will be used to document results at the clinic visits and a study-provisioned smart phone or study application on the subject's own smartphone will be used to document results at the subject's home/away from clinic over 14 days of study drug treatment.

19.3. Laboratory Results

Laboratory tests (clinical chemistry, hematology and urinalysis) will be analyzed by a certified laboratory (ACM) and reported to the clinic site as results are generated. The Investigator will review and comment on any laboratory value reported outside the normal range provided by the laboratory. The laboratory data must be signed and dated and kept in the study subject file at the site for the Sponsor and will represent the source data.

20. STUDY DOCUMENTATION

20.1. Source Documents

Source documents may include, but are not limited to, laboratory reports, ECG tracings, clinic notes or pharmacy records and any other similar reports or records of any procedure performed in accordance with the protocol. Source documents may also include eCRFs or electronic devices when information is recorded directly onto such forms or devices.

Whenever possible, the original recording of an observation should be retained as the source document; however, a photocopy is acceptable provided that it is a clear, legible, and exact duplication of the original document.

20.2. Access to Records

As required by the International Council for Harmonisation-Good Clinical Practice (ICH-GCP) guidelines and regulatory authorities the Investigator will allow Sponsor's representative(s) direct access to all pertinent medical records in order to allow for the verification of data gathered in the eCRFs and for the review of the data collection process. The records, including source documentation, must also be available for inspection by relevant regulatory health authorities.

20.3. Retention of Records

According to ICH guidelines, essential documents should be retained for a minimum of 2 years after the last approval of a marketing application in an ICH region and until there are no pending or contemplated marketing applications in an ICH region or at least 2 years have elapsed since the formal discontinuation of clinical development of the Investigational Product. However, these documents should be retained for a longer period if required by the applicable legal requirements.

21. INSTITUTIONAL REVIEW BOARD (IRB)

The final study protocol, including the final version of the Informed Consent Form, must be approved or given a favorable opinion in writing by an IRB or IEC as appropriate. The Investigator must submit written approval to the Sponsor before he or she can enroll any patient/subject into the study.

The Principal Investigator is responsible for informing the IRB of any amendment to the protocol in accordance with local requirements. In addition, the IRB must approve all advertising used to recruit patients for the study. The protocol must be re-approved by the IRB upon receipt of amendments and annually, as local regulations require.

The Principal Investigator is also responsible for providing the IRB with reports of any reportable serious adverse drug reactions from any other study conducted with the investigational product. The Sponsor will provide this information to the Principal Investigator.

Progress reports and notifications of serious adverse drug reactions will be provided to the IRB according to local regulations and guidelines.

22. ETHICAL CONDUCT OF THE STUDY

The study will be performed in accordance with ethical principles that have their origin in the Declaration of Helsinki and are consistent with ICH/GCP, applicable regulatory requirements, and the Neurana Pharmaceuticals, Inc. policy on bioethics.

The procedures set out in this study protocol pertaining to the conduct, evaluation, and documentation of this study are designed to ensure that Neurana Pharmaceuticals, Inc., its authorized representative, and Investigator abide by GCP, as described in ICH Guideline E6 and in accordance with the general ethical principles outlined in the Declaration of Helsinki.

23. INFORMED CONSENT

It is the responsibility of the Investigator to give each potential study subject, prior to inclusion into the study, full and adequate verbal and written information regarding the objectives and procedures of the study. The study subjects must be informed about their right to withdraw from the study at any time. It is the responsibility of the Investigator (who may delegate this task to other members of the study team) to obtain signed informed consent from all study subjects before any study related assessments are performed. Consent must be documented by the subject's dated signature on an informed consent form along with the dated signature of the person conducting the consent discussion. A copy of the signed and dated consent form should be given to the subject before participation in the study.

The initial informed consent form and any subsequent revised written informed consent form, and any written information provided to the subject must receive the IRB approval/favorable opinion in advance of use. In the event of a revised informed consent, all ongoing subjects and newly enrolled subjects should be administered and sign the most current IRB-approved ICF.

24. CONFIDENTIALITY

24.1. Confidentiality of Data

By signing this protocol, the Investigator affirms to the Sponsor that information furnished to the Investigator by the Sponsor will be maintained in confidence and such information will be divulged to the IRB and Food and Drug Administration (FDA), or similar or expert committee; affiliated institution; and employees only under an appropriate understanding of confidentiality with such board or committee, affiliated institution and employees. Data generated by this study will be considered confidential by the Investigator, except to the extent that it is included in a publication with prior approval of the Sponsor.

